8.4 ADVERSE EVENTS AND SERIOUS ADVERSE EVENTS

8.4.1 Definition of Adverse Event

Adverse Event (AE) means any untoward medical occurrence associated with the use of an intervention in humans, whether or not considered intervention-related (21 CFR 312.32 (a)).

8.4.2 Definition of Serious Adverse Events (SAE)

An adverse event (AE) or suspected adverse reaction is considered "serious" if, in the view of either the investigator or sponsor, it results in any of the following outcomes: death, a life-threatening adverse event, inpatient hospitalization or prolongation of existing hospitalization, a persistent or significant incapacity or substantial disruption of the ability to conduct normal life functions, or a congenital anomaly/birth defect. Important medical events that may not result in death, be life-threatening, or require hospitalization may be considered serious when, based upon appropriate medical judgment, they may jeopardize the participant and may require medical or surgical intervention to prevent one of the outcomes listed in this definition. Examples of such medical events include allergic bronchospasm requiring intensive treatment in an emergency room or at home, blood dyscrasias or convulsions that do not result in inpatient hospitalization, or the development of drug dependency or drug abuse.

8.4.3 Classification of an Adverse Event

8.4.3.1 Severity of Event

For adverse events (AEs) not included in the protocol defined grading system, the following guidelines will be used to describe severity.

- **Mild** – Events require minimal or no treatment and do not interfere with the participant's daily activities.
- **Moderate** – Events result in a low level of inconvenience or concern with the therapeutic measures. Moderate events may cause some interference with functioning.
- **Severe** – Events interrupt a participant's usual daily activity and may require systemic drug therapy or other treatment. Severe events are usually potentially life-threatening or incapacitating. Of note, the term "severe" does not necessarily equate to "serious".]

Abbreviated Title: [¹⁸F]SF12051 in Healthy Subjects

Version Date: 12/05/23

8.4.3.2 Relationship to Study Intervention

All adverse events (AEs) must have their relationship to study intervention assessed by the investigator who examines and evaluates the participant based on temporal relationship and his/her clinical judgment. The degree of certainty about causality will be graded using the categories below. In a clinical trial, the study product must always be suspect.

- **Definitely Related** – There is clear evidence to suggest a causal relationship, and other possible contributing factors can be ruled out. The clinical event, including an abnormal laboratory test result, occurs in a plausible time relationship to study intervention administration and cannot be explained by concurrent disease or other drugs or chemicals. The response to withdrawal of the study intervention (dechallenge) should be clinically plausible. The event must be pharmacologically or phenomenologically definitive, with use of a satisfactory rechallenge procedure if necessary.
- **Probably Related** – There is evidence to suggest a causal relationship, and the influence of other factors is unlikely. The clinical event, including an abnormal laboratory test result, occurs within a reasonable time after administration of the study intervention, is unlikely to be attributed to concurrent disease or other drugs or chemicals, and follows a clinically reasonable response on withdrawal (dechallenge). Rechallenge information is not required to fulfill this definition.
- **Potentially Related** – There is some evidence to suggest a causal relationship (e.g., the event occurred within a reasonable time after administration of the trial medication). However, other factors may have contributed to the event (e.g., the participant's clinical condition, other concomitant events). Although an AE may rate only as "possibly related" soon after discovery, it can be flagged as requiring more information and later be upgraded to "probably related" or "definitely related", as appropriate.
- **Unlikely to be related** – A clinical event, including an abnormal laboratory test result, whose temporal relationship to study intervention administration makes a causal relationship improbable (e.g., the event did not occur within a reasonable time after administration of the study intervention) and in which other drugs or chemicals or underlying disease provides plausible explanations (e.g., the participant's clinical condition, other concomitant treatments).
- **Not Related** – The AE is completely independent of study intervention administration, and/or evidence exists that the event is definitely related to another etiology. There must be an alternative, definitive etiology documented by the clinician.]

8.4.3.3 Expectedness

The PI will be responsible for determining whether an adverse event (AE) is expected or unexpected. An AE will be considered unexpected if the nature, severity, or frequency of the event is not consistent with the risk information previously described for the study intervention.

8.4.4 Time Period and Frequency for Event Assessment and Follow-Up

The occurrence of an adverse event (AE) or serious adverse event (SAE) may come to the attention of study personnel during study visits and interviews of a study participant presenting for medical care, or upon review by a study monitor.

All AEs including local and systemic reactions not meeting the criteria for SAEs will be captured on the appropriate case report form (CRF). Information to be collected includes event description, time of onset, clinician's assessment of severity, relationship to study product (assessed only by those with the training and authority to make a diagnosis), and time of resolution/stabilization of the event. All AEs occurring while on study must be documented appropriately regardless of relationship. All AEs will be followed to adequate resolution.

Any medical condition that is present at the time that the participant is screened will be considered as baseline and not reported as an AE. However, if the study participant's condition deteriorates at any time during the study, it will be recorded as an AE.

Changes in the severity of an AE will be documented to allow an assessment of the duration of the event at each level of severity to be performed. AEs characterized as intermittent require documentation of onset and duration of each episode.

Credentialed clinicians will record all reportable events with start dates occurring any time after informed consent is obtained until 7 (for non-serious AEs) or 30 days (for SAEs) after the last day of study participation. At each study visit, the investigator will inquire about the occurrence of AE/SAEs since the last visit. Events will be followed for outcome information until resolution or stabilization.

8.4.5 Adverse Event Reporting

Non-SAEs will be reported to the ISM (annually), to the IRB at the time of Continuing Review and to the Sponsor at regular intervals per request.

8.4.6 Serious Adverse Event Reporting

It is both the Principal Investigator's (PI) and the Sponsor's responsibility to ensure the safety of those on the clinical trial. The PI is responsible for tracking adverse events during the study and providing adverse events lists to the Sponsor at regular intervals per request. These may be requested quarterly and will be requested no less than once a year at the time of IND annual report to the FDA. ALL AEs that are collected, as determined by the written protocol, should be tracked in the ORSC RSS' template AE Tracker or similar document. If the sponsor determines that adverse events are occurring more frequently or more severely than the written protocol had expected and/or anticipated, this should be submitted in an IND Safety Report, as described below. In addition, the PI is responsible for updating the Sponsor about known risks from the drug, as discovered from literature searches or other means.

In accordance with the requirements of 21 CFR 312.32, the PI or designee will report all SAEs, whether or not these are considered related to the investigational drug or study intervention, that occur throughout the study to the Sponsor, including those events listed in the protocol or Investigator's Brochure as anticipated to occur, as follows:

Deaths: within 24 hours of the investigator's awareness*

All other SAEs: within 48 hours of the investigator's* awareness

All AEs will be sent to the Sponsor quarterly, unless requested more or less frequently, for submission to the FDA in the IND Annual Report.

*“Investigator's awareness” includes awareness by anyone on the study team

The PI will immediately report all deaths and SAEs to the Sponsor by disclosing all event-related information in a completed MedWatch Form 3500A. This form should include the IND number, protocol number, PI name, and an assessment on the reasonable possibility of a relationship between the event and the study drug or intervention. **MRNs should NOT be included on this form.** The completed MedWatch Form 3500A will be sent **ENCRYPTED** to the Clinical Director/CEO and/or designated medical monitor with a copy to the NIH Office of Research Support & Compliance (ORSC) Regulatory Support Section.

The Clinical Director/CEO and/or designated medical monitor will be responsible for determining whether the event is reportable to the FDA as an IND Safety Report if it is a serious, unexpected, and suspected adverse reaction (SUSAR). If the sponsor determines the SAE meets the criteria of a SUSAR, the ORSC will submit an Initial IND Safety Report to the FDA no later than 15 calendar days after the PI's notification of the event to the Sponsor. Deaths or life-threatening events will be reported to the FDA no later than 7 calendar days after the PI's notification of the event to the Sponsor. The Sponsor will submit any relevant additional information in a Follow-up IND Safety Report no later than 15 calendar days after receiving the information. All SAEs will be monitored until satisfactory resolution. All AEs and SAEs will be documented on appropriate study records.

8.4.7 NIH Intramural IRB Reporting of IND Safety Reports

Only IND Safety Reports that meet the definition of an unanticipated problem or is new information that might affect the willingness of subjects on the NIH study to enroll or remain in the study will need to be reported to the NIH Intramural IRB.

8.4.8 Events of Special Interest

None.

8.4.9 Reporting of Pregnancy

Participants will be excluded if they are or may become pregnant.

8.5 UNANTICIPATED PROBLEMS

8.5.1 Definition of Unanticipated Problems (UP)

Any incident, experience, or outcome that meets all of the following criteria:

- Unexpected in terms of nature, severity, or frequency given (a) the research procedures that are described in the protocol-related documents, such as the Institutional Review Board (IRB)-approved research protocol and informed consent document; and (b) the characteristics of the participant population being studied; and
- Related or possibly related to participation in the research (“possibly related” means there is a reasonable possibility that the incident, experience, or outcome may have been caused by the procedures involved in the research); and
- Suggests that the research places participants or others (which many include research staff, family members or other individuals not directly participating in the research) at a greater risk of harm (including physical, psychological, economic, or social harm) than was previously known or expected.

8.5.2 Unanticipated Problem Reporting

The investigator will report unanticipated problems (UPs) to the NIH Institutional Review Board (IRB) as per Policy 801.

9 STATISTICAL CONSIDERATIONS

9.1 STATISTICAL HYPOTHESIS

Primary Endpoint(s): We hypothesize that [¹⁸F]SF12051 will show strong binding affinity for TSPO regardless of genotype.

Secondary Endpoint(s): We hypothesize that the retest variability and reliability of [¹⁸F]SF12051 will allow its use in clinical protocols.

We hypothesize that the dosimetry and biodistribution of [¹⁸F]SF12051 will be similar to that of other ¹⁸F tracers.

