1.1 SYNOPSIS

| | |
|---|---|
| Title: | Assessment of [¹⁸ F]SF12051 for Imaging the 18-kDa Translocator Protein (TSPO) in Brain and Whole Body of Healthy Subjects |
| Study Description: | This study is intended to provide information on the novel [¹⁸ F]SF12051 radioligand and its ability to localize and measure TSPO in the brain and body of healthy individuals. |
| Objectives: | 
Primary Objective: To study the brain uptake of [¹⁸F]SF12051 and perform kinetic modeling of the [¹⁸F]SF12051 in the three different TSPO genotypes.
 
Secondary Objectives: To study the brain retest characteristics, biodistribution and dosimetry of [¹⁸F]SF12051 in healthy subjects.
 |
| Endpoints: | 
Primary Endpoint: The distribution volume of the radioligand and stability over time calculated with compartmental modeling, attention paid to differences in mean distribution volumes between TSPO genotypes for determining genotype sensitivity.
 
Secondary Endpoints: Retest variability and reliability and organ-time-activity curves to determine biodistribution and dosimetry.
 |
| Study Population: | Up to forty-five (45) healthy male and female volunteers (18 years and older) of the three different TSPO genotypes for brain and whole-body imaging. |
| Phase: | N/A |
| Description of Sites/Facilities | Screening and PET imaging will be performed at the NIH Clinical Center. |
| Enrolling Participants: | |
| Description of Study Intervention: | Arterial line, PET scan, and brain MRI scan for absolute quantification of TSPO. Blood drawn from all subjects to determine TSPO genotype. |
| Study Duration: | 3 years |
| Participant Duration: | 1-4 visits, 2-6 hours per visit. |

Abbreviated Title: [¹⁸F]SF12051 in Healthy Subjects

Version Date: 12/05/23

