2 INTRODUCTION

2.1 STUDY RATIONALE

The mitochondrial protein 18-kDa translocator protein (TSPO) is highly expressed in phagocytic inflammatory cells, including activated microglia and reactive astrocytes in the brain and macrophages in the periphery (1,2). Although numerous positron emission tomography (PET) radioligands have been developed to image TSPO, several limitations have restricted their clinical utility for quantifying inflammation in the brain. Of these radioligands, the first-generation TSPO radioligand ¹¹C-(R)-PK11195 has been the most extensively studied. ¹¹C-(R)-PK11195 has high affinity to TSPO; however, its utility is limited by low ratio of specific-to-nondisplaceable uptake (i.e., nondisplaceable binding potential, BP_{ND}) in the brain as well as the relatively short half-life of ¹¹C (20 minutes) (3,4). Second-generation radioligands, such as ¹¹C-PBR28, offer a higher in vivo TSPO-specific signal but suffer from sensitivity to the single nucleotide polymorphism (SNP) rs6971 (5,6), which splits the human population into high-, mixed-, and low-affinity binders (HAB, MAB, LAB). LAB have too little TSPO binding to measure. This SNP sensitivity both complicates the interpretation of results and requires genotyping of study participants to exclude LABs before imaging.

Recently, we synthesized a new TSPO ligand, [¹¹C]ER176, which, although still sensitive to genotype differences, has enough specific binding to allow the imaging of low binders as well (7). This has important practical advantages, because low binders would not need to be excluded from clinical protocols and genotyping could be performed at the end of the protocol for all subjects at once, rather than case-by-case before scanning takes place. However, ER176 is labeled with ¹¹C, and therefore would not be available to centers without a cyclotron on site. The rationale of this study is to determine whether a novel ¹⁸F-labeled radioligand, [¹⁸F]SF12051,

whose structure is similar to that of [¹¹C]ER-176, has comparable or improved efficacy for imaging TSPO and/or dependence on TSPO genotype.

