We predict that the new ¹⁸F-radioligand will be like [¹¹C]ER176 and, therefore, that it *will* be sensitive to genotype. Even though [¹¹C]ER176 is sensitive to genotype, it provides time-stable values of receptor binding. Thus for [¹¹C]ER176 and presumably for [¹⁸F]SF12051, LAB subjects need not be excluded a priori, but the results must be corrected a posteriori. If [¹⁸F]SF12051 values of receptor binding are unstable in LABs, it would still be an improvement over current ¹¹C-radioligands and can be used at more sites because of the longer half-life of ¹⁸F compared to ¹¹C.”

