4 STUDY DESIGN

4.1 OVERALL DESIGN

- **Site:** This single-site study will be conducted at the NIH Clinical Center.
- **Hypothesis:** We hypothesize that [¹⁸F]SF12051 will have satisfactory distribution regardless of genotype, acceptable retest variability and reliability, and dosimetry typical of ¹⁸F-labeled radioligands.
- **Phase:** Phase 1
- **Type of Design:** Study is neither randomized nor placebo-controlled; exploratory study.
- **Study Groups:** Healthy volunteers
- **Study intervention:** Brain and body PET scans with [¹⁸F]SF12051 and brain MRI.
- **Interim Analysis:** None
- **Stratifications:** None

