9.4.7 Sub-Group Analyses

The different genotype groups will be analyzed separately.

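### The genotype difference in V_T belongs to the primary endpoint, but no between-genotype estimate with a confidence interval is planned, and the primary hypothesis leaves its meaning open

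*Combined protocol and SAP*

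**What the plan says.** - **Endpoint.** The synopsis defines the primary endpoint as the distribution volume and its stability over time, with "attention paid to differences in mean distribution volumes between TSPO genotypes for determining genotype sensitivity".
- **Prediction.** Section 2.1 expects the tracer to resemble ER176 and therefore "that it *will* be sensitive to genotype". Its practical consequence is that "LAB subjects need not be excluded a priori, but the results must be corrected a posteriori".
- **Hypotheses.** Section 9.1 states that the tracer "will show strong binding affinity for TSPO regardless of genotype". Section 4.1 states that it "will have satisfactory distribution regardless of genotype". Neither defines strong or satisfactory, or gives a margin.
- **Sample size.** Section 9.2 works from a difference test with 10 per group, 80% power and alpha 0.05. It gives 40% of the HAB mean as the detectable difference, then restates that figure as what a difference must exceed to be significant.
- **Analysis.** Section 9.4.2 summarises V_T as mean and SD. Section 9.4.7 adds "The different genotype groups will be analyzed separately". Section 9.4.8 plans no exploratory analyses. No contrast, ratio or confidence interval between genotypes is named.

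**The concern.** The plan raises a between-group question and answers it with within-group summaries. Genotype sensitivity is a contrast, and nothing commits the investigators to estimating it or showing how uncertain it is. The one yardstick available, the 40% figure in 9.2, is a detectable difference at 80% power. It is not the smallest observed difference that would reach significance, and it is larger than the HAB-MAB difference already seen with ER176.

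If the HAB-MAB difference comes out non-significant or below 40%, a reader holding the 9.1 wording has no protocol text in section 9 that says how to take it. The practical stake is the genotype correction that section 2.1 says is needed. It could be dropped, or thought unnecessary, on data that cannot support that step.

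**Working it through.** **Inputs from 9.2:** HAB mean V_T 4.5 mL/cm³, SD 1.4 (ER176, n = 9); HH 40% higher than HL; the same SD assumed for the new tracer; 10 per group; power 80%; alpha 0.05. Sidedness is not stated, so two-sided is assumed.

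**1. The plan's own figure.** The standard error of a pairwise difference is 1.4 × √(2/10) = 0.626. By the normal approximation, the detectable difference is (1.960 + 0.842) × 0.626 = 1.754, and 1.754 / 4.5 = 39.0%. With the noncentral t it is 41.2%. The stated 40% is reproduced. Section 9.2 attributes the power analysis to PBR28 scans, but the ER176 inputs give this answer.

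**2. The ER176 difference on the same base.** If HH is 40% higher than HL, then HL = 4.5 / 1.4 = 3.21. The difference is 1.29, and 1.29 / 4.5 = 28.6% of the HAB mean. The two 40% figures in 9.2 have different denominators: one is relative to HL, the other to HAB.

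**3. Precision.** The 95% half-width for a pairwise difference is 2.101 × 0.626 = 1.32 mL/cm³, or 29% of the HAB mean. That is also the smallest observed difference that would be significant at this SD, so the 40% in 9.2 is not the significance threshold. The half-width is slightly larger than the whole ER176 HAB-MAB difference.

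**4. Chance of a null HAB-MAB result if the tracer behaves like ER176 (10 per group).**

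| Variance model | Power | Non-significant |
|---|---|---|
| Constant SD 1.4, noncentral t | 49% | 51% |
| SD proportional to mean, Welch test, simulated | 60% | 40% |
| Constant CV, log scale | 65% | 35% |

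For the last row, CV = 1.4 / 4.5 = 0.311, the log-scale SD is √ln(1 + 0.311²) = 0.304, and the effect is ln 1.40 = 0.336. With 11 per group, close to 34 / 3, constant-SD power is 54%.

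**5. The 40% rule applied to the observed difference.** The threshold is 0.40 × 4.5 = 1.8. The chance of exceeding it when the true difference is 1.29 is P(Z > (1.8 − 1.286) / 0.626) = P(Z > 0.82) ≈ 0.21. An ER176-sized difference would fall short about 79% of the time (constant SD, HAB mean fixed at 4.5).

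**6. What a ratio would look like.** The log-scale interval factor is exp(2.101 × 0.304 × √0.2) = 1.33. An observed HAB/MAB ratio of 1.40 would have a 95% interval of 1.40 / 1.33 to 1.40 × 1.33, about 1.05 to 1.86.

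**The case against.** The strongest reply is that 9.1 and 2.1 do not conflict. Binding can be strong in every genotype and still differ between them, which is how sections 2.1 and 2.2.1 describe ER176. This stands. A reader might infer a contradiction, but the text supports only an ambiguity: 9.1 does not say which meaning it intends.

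A reader might also infer that a null test would count as success. No section says so. Section 9.4 names no genotype test, and 2.1 already commits to later correction. The point that remains is that section 9 contains nothing to prevent the misreading, while 9.2 supplies a threshold that invites it.

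It would also be too strong to say that nothing useful is planned. Section 9.4.1 covers identifiability and time stability, which bear directly on whether V_T is measurable in each genotype. Ratios and intervals could be derived from the planned summaries. What is missing is their prespecification.

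Nor do the documents show that an overall null across the three genotypes is likely. They give no ER176 LAB value. Under assumed values (10 per group, SD 1.4, unadjusted tests), neither HAB contrast would be significant in about 34% of trials if LAB equals MAB, and in about 2% if V_T falls linearly from HAB to LAB.

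Finally, section 2.1 asks whether the tracer "has comparable or improved efficacy for imaging TSPO and/or dependence on TSPO genotype" relative to ER176, and a reader might call the missing comparison a failure of the plan. It is rationale only. No objective or endpoint includes it, section 4.1 calls the study exploratory, and V_T contains non-displaceable uptake, so ratios across tracers are not clean measures of genotype sensitivity.

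**Conclusion.** The point holds in a limited form. The plan does not prespecify an estimate, with its uncertainty, of the genotype differences in its own primary endpoint, and 9.1 does not say what it claims about genotype. For HAB versus MAB, a null result would occur in about 35% to 51% of trials with a tracer as genotype-sensitive as ER176, so it could not tell the two situations apart.

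This rests on the ER176 mean, SD and HH/HL ratio in 9.2 carrying over to the new tracer, on 10 evaluable participants per group, and on a two-sided unadjusted 5% test. The range reflects the choice of variance model. Nothing is claimed about the size of the LAB contrast. The change should be made, but the study design and sample size need not alter for it.

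**What to change.** - **9.4.2:** name the HAB/MAB and HAB/LAB V_T ratios, estimated on the log scale with 95% confidence intervals, as the primary genotype-sensitivity estimates. Keep mean and SD by genotype as description.
- **4.1 and 9.1:** say that V_T is expected to be quantifiable and time-stable in all three genotypes, and that genotype sensitivity is expected and will be estimated.
- **Section 9:** state that a genotype difference that is non-significant, or below 40%, will not be read as independence from genotype.
- **Optional:** set the HAB/MAB ratio descriptively beside the ER176 ratio of 1.40, labelled as non-concurrent and across tracers. The documents give no LAB value with which to do the same for HAB/LAB.

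The cost is protocol wording and one small table, with no added participants or scans. The intervals will be wide, and that width is what the reader needs to see.
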